4.4 Recruitment Procedures

All patients enrolled in the pediatric acute liver failure registry will be offered an opportunity to participate in this treatment trial, if potentially eligible. The clinical center principal investigator/co-investigator will inform the parent/guardian about the purpose of the study, procedures involved, the randomization process and measures taken to protect the subject and confidentiality. The parent/guardian will be informed of the risks and potential benefits of the study and of the child's rights as a research subject. All questions will be answered prior to obtaining their signature on the informed consent document. Each site will follow their respective state laws regarding the definition of a legal guardian and the right of the legal guardian to provide consent for research.

4.4.1 Informed Consent:

Informed written consent from the patient's parent or legal guardian is obtained for the collection of data and biospecimens as part of the multi-center PALF registry already in operation. A separate informed consent for the NAC study will be documented by the use of a written consent form approved by the IRB and signed by the patient's parent or legal guardian. Children less than 18 who are developmentally able to sign his or her name, and whose clinical condition, allows will be asked to assent in accordance with local IRB practices. A copy shall be given to the person signing the form. The consent form must embody the legally required elements of informed consent. The clinical center principal investigator shall give the patient's representative adequate time to read the form prior to signature. The parent or legal guardian can withdraw the patient from the study at any time, and this decision will not influence the treatment otherwise offered. It is not anticipated that any special groups will be enrolled in the study in any proportion other than those who are

representative of the US population. The NIH guidelines on the inclusion of females and minorities as subjects in clinical research will be observed.

4.5 Risk/Benefit Ratio

A possible risk is a breach of confidentiality, although steps have been taken to minimize such an occurrence. All information collected for this research study will be kept confidential. Patients' names will be used only for the informed consent form and medical chart reviews. Patients will be given unique study identifiers, which will be written on all data collection forms and biospecimens. In addition, data collection forms will be kept in secured, locked files. Known breaches of confidentiality will be reported to NIDDK.

The main adverse event reported in previous studies of NAC was a rare hypersensitivity reaction, manifested by rash or wheezing, and occurring with increased frequency in patients with a previous asthmatic diathesis. In each instance, use of intravenous anti-histamine (diphenhydramine) or corticosteroids aborted the attack and no instances of severe reactions have been reported. In most instances, the infusions were not discontinued and all symptoms resolved once diphenhydramine was instituted and the rate of infusion slowed.

Unusual events and anaphylactic reactions that occur during the seven day treatment period will be reported on a separate adverse event reporting sheet, and faxed to the Data Coordinating Center within 24 hours of knowledge of event. All Serious Adverse Event (SAE) reports received by the Data Coordinating Center will be forwarded to the Medical Safety Officer, the Data Safety and Monitoring Board (DSMB), the NIDDK project officer, and the IND holder. Serious adverse events that occur during the course of the trial and that meet criteria for expedited reporting will be forwarded to the FDA within 24 hours of receipt.

A DSMB, with members appointed by the NIDDK, consists of individuals who are independent of the institutions and investigators participating in the PALF study and who have no financial ties to the outcome of the trial. The ongoing review of the data by this independent committee assures the investigators and the NIDDK that the trial can continue without jeopardizing patient safety. The DSMB charter was developed by the NIDDK. The data and safety monitoring plan was approved by the DSMB. The roster and charter of the DSMB members will be provided to investigators participating in the study for submission to their IRB.

The DSMB will review the study protocol, recommend recruitment continuation, monitor all aspects of the study (e.g., recruitment, protocol deviations, adverse events, site visit summaries, data quality, attrition, descriptive characteristics), and recommend protocol modifications, which may include early study termination. Quarterly reports will be prepared by the DCC. Tables showing study progress overall and stratified by clinical center will be presented. These will include recruitment, protocol deviations, attrition, adverse events, and data quality. There will also be a table providing descriptive characteristics of the study sample. The DCC will maintain a cumulative summary of adverse events overall and stratified by serious/non-serious status to be forwarded to the DSMB quarterly. The DSMB will meet twice yearly, once in person and once via teleconference to review the data. A closed session will be held to review safety, efficacy, and data quality. Results of the interim data analysis will be viewed in closed session. Based on the data presented, the DSMB will recommend continuation or termination of the study. A summary of the DSMB findings will be forwarded to all investigators for submission to their respective IRBs.

NAC Study Protocol

In the future, other young people with acute liver failure could benefit from the results of this research. Information gained from this research could lead to improved medical care for them. However, benefits to other young people with acute liver failure will not be known until all of the information has been collected and analyzed.

5.0 Costs and Payments

5.1 Research Study Costs

The patient's insurance provider will not be billed for any procedures performed solely for the purpose of this research study. Expenses resulting from standard care for medical problems are the responsibility of the patient, patient's guardian, or the patient's insurance provider or government program. There are no funds available to pay for lost time away from work and other activities, lost wages, or child care expenses.

5.2 Research Study Payments

There are no payments or other remunerations to the research subjects.

NAC Study Protocol

6.0 Appendices

[figure not shown]

32. Modig, J. and R. Sandin, *Haematological, physiological and survival data in a porcine model of adult respiratory distress syndrome induced by endotoxaemia. Effects of treatment with N-acetylcysteine*. Acta Chir Scand, 1988. **154**(3): p. 169-77.
33. Bailey, B. and M.A. McGuigan, *Management of anaphylactoid reactions to intravenous N-acetylcysteine*. Ann Emerg Med, 1998. **31**(6): p. 710-5.

NAC Study Protocol

6.2: Pediatric NAC Protocol

The overall survival rate at one year in this model is 69.0% (45.0% + 24.0%) in the placebo arm and 86.5% (55.0% + 31.5%). Estimating the total number of planned analyses at 6 using O'Brien Fleming boundaries for both H_0 and H_1 , a minimum of 184 patients (92 in each arm) will provide 80% power using a two-sided log-rank test (assuming proportional hazards) and an overall $\alpha = 0.054$ (if all 6 interim analyses are performed).

6.3 Overall patient management and the NAC trial

Standard treatment for acute liver failure includes placement in an intensive care unit and close observation for infection, bleeding, brain swelling, and other common complication of the condition. Supportive measures include fluids by vein, antibiotics, blood products, and a breathing support machine as necessary.

Initial management will be at the discretion of each institution, but general guidelines have been established during early meetings of the PALF Study Group. Triage for establishing diagnosis and degree of severity will be along standard clinical parameters.

Every effort will be made to establish the diagnosis within eight hours of admission to the hospital at which time informed consent can be sought from the child's parent or legal guardian. Once consent is obtained, patients will be allocated to treatment with NAC or placebo for the following 7 days. The intensive care treatment of acute liver failure patients will otherwise be unaffected. This treatment generally includes:

- Maintenance of blood glucose levels > 90 mg/dl via dextrose infusion (range 5%-20%) that is evaluated by blood glucose tests at regular intervals.
- Adequate fluid replacement and balance, as assessed by clinical inspection, electrolytes, central venous or pulmonary capillary wedge pressure.
- Nasogastric tube placement and treatment with H₂-receptor antagonist or proton pump inhibitor.
- Close monitoring of possible infections. Proper antibiotics if infected and prophylactic antibiotics (cephalosporins) to all patients with deep coma grade III or grade IV.
- Head elevation to 20°, if coma grade III or IV.
- Mechanical ventilation and induced hyperventilation in patients with deep coma grade III and coma grade IV.
- Infusion of mannitol if ICP >25 mmHg or clinical signs of intracranial hypertension (unstable mean arterial pressure with hypertension, irregular breathing, pupillary dilatation, decerebrate movements).

In general, clinical and laboratory parameters in the clinical center are measured at least twice daily, and it should be unnecessary to take special blood samples or any samples more often than twice daily in regard to monitoring the NAC study. There are daily assessments of laboratory parameters and intensive care measures such as intubations and the need for circulatory support.

LIVER TRANSPLANTATION:

In general, most patients advancing to grade III-IV encephalopathy are listed for liver transplantation unless there are contra-indications. Criteria for transplantation will be those usually practiced at each transplant center, but essentially conform to those leading to placement as UNOS status 1.

NAC Study Protocol

6.4 NAC checklist prior to entering and randomizing a patient

A Multi-center Study of the Safety and Efficacy of N-acetylcysteine in the Treatment of Acute Liver Failure in Pediatric patients not Caused by Acetaminophen

Investigators:	Phone/Pager:	Nights/Weekends

Patient Name: _____ MRN: _____ Study No: _____

Inclusion Criteria:

1. Enrollment in PALF registry
2. Informed consent obtained from the patient (when patient is 14-17 years of age or <17 and developmentally able to sign his or her name), parent, or guardian.

Exclusion Criteria:

1. Acute Acetaminophen toxicity
2. Pregnancy
3. Known malignancy.
4. Patient is on a liver support device
5. Sepsis
6. Signs of cerebral herniation.
7. Intractable hypotension defined as systolic BP < 85 mm Hg or hypotension that requires treatment with inotropic drugs, other than renal dosing dopamine.

Needed on each patient prior to randomization

1. Signed consent form
2. Patient weight (kg): _____
3. Coma Grade (0, I, II, III or IV): _____
4. Age: _____

Randomizing patient

1. Fax a copy of the drug order form (with patient weight in kg, coma grade, and age), and if needed, the signed consent form to the Investigational Drug Pharmacy at: _____

2. Contact IDS Pharmacist: _____ Weekdays, after hours & weekends: _____

NAC Study Protocol

6.5: Sample Order Form

CHILDREN'S MEDICAL CENTER OF DALLAS [name] • [contact] Physician Orders Generic equivalent drugs may be used unless otherwise specified	MED REC NO. _____ ACCT NO. _____ PATIENT _____ DATE _____ LOCATION _____ DOB _____
	ALLERGIES:  NKA- No known allergies  (Specify) _____ Weight (kg) _____
DATE AND TIME	ORDERS Copies (Do Not Write Orders If No Copies Remain, Begin New Form) Remaining
Acute Liver failure N- Acetylcysteine vs. Placebo Study	
IRB File No: 0502-296	
Principal Investigator:	
Patient Weight:	
Patient age (years and months) at randomization	
Patient's exact coma grade at randomization	
Study Orders:	
Infuse study solution at a rate of cc/hr (5cc/kg/24hrs) for 7 days	
Pharmacy to randomize patient to receive either N- Acetylcysteine 30 mg/ml in D5W or Placebo Solution (D5W alone)	
Notify physician for:	
Urticaria	
Respiratory distress	
Meds	
Benadryl mg (1mg/kg) for IV use to be available for bronchospasm, hives	
Continue all other evaluations and treatment unchanged.	
MD Signature	

6.6: Handling Adverse Reactions to N-acetylcysteine (NAC)

NAC is a very safe drug and has been used extensively by mouth and intravenously for the treatment of acetaminophen poisoning. The main adverse event reported in previous studies of NAC was a rare hypersensitivity reaction: rash or wheezing, which occurs with increased frequency in asthmatics.

Suggested treatment:

1-1.25 mg/kg diphenhydramine (Benadryl) intravenously slowly.

1 mg/kg methylprednisolone (Solumedrol) stat intravenously (max dose 1.0 gm)

Epinephrine as treatment of anaphylaxis might be considered, although this has not been reported to be needed in the past. Dose: 0.01 cc/kg (1:1,000) subcutaneously (max 0.3 cc) may repeat every 15 minutes

Resumption of medication:

If minor allergic reaction develops, discontinue medication for 2 hours then cautiously restart at a slow rate, continuing to increase rate to full dose if no reaction observed.

Other pointers:

Continuous EKG monitoring is recommended in light of one report of minor EKG abnormalities. Since acute liver failure carries a high mortality, it will be difficult in one sense to recognize evidence of additional toxicity due to NAC, in light of the multi-organ failure picture that patients typically develop. Please report any suspicious events such as the development of adult respiratory distress syndrome (ARDS), gastrointestinal bleeding, etc.

Serious Adverse Event Reporting

Unusual events and the occurrence of anaphylactic reactions that occur during the seven day treatment period will be reported on a separate adverse event reporting sheet, and faxed to the Data Coordinating Center within 24 hours of knowledge of event. All Serious Adverse Event (SAE) reports received by the Data Coordinating Center will be forwarded to the Medical Safety Officer, the Data Safety and Monitoring Board (DSMB), the NIDDK project officer, and the IND holder. Serious adverse events that occur during the course of the trial and that meet criteria for expedited reporting will be forwarded to the FDA within 24 hours of receipt.

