2.1.4 Why Choose N-acetylcysteine?

After acetaminophen overdose, N-acetylcysteine replenishes mitochondrial and cytosolic glutathione stores, and has been shown in patients and in experimental animals to prevent or ameliorate the degree of injury and cell death [21]. Intravenous or oral NAC improves survival in patients with acetaminophen-induced ALF [18]. Evidence that NAC may benefit the patient, even when given as late as 72 hours after overdose, led to its use in non-acetaminophen ALF cases [22]. A small uncontrolled study showed improvement in cardiovascular hemodynamics and oxygen transport in both acetaminophen (n=12) and non-acetaminophen (n=8) patients [23]. Mean arterial pressure, oxygen consumption, and oxygen delivery increased, as did the oxygen extraction ratio. As a result, intravenous NAC has been incorporated into the management strategy used at Kings and elsewhere as treatment for all acute liver failure, but has never been subjected to a controlled trial. A second study confirmed the earlier findings concerning hemodynamics, and showed a significant increase in cyclic guanine monophosphate (cGMP) levels suggesting that NAC may cause vasodilatation by increasing soluble guanylate cyclase activity [24]. However, a more recent study from Edinburgh failed to demonstrate improved hemodynamics with NAC: patients with ALF in Grade IV coma on a ventilator were given intravenous NAC with no improvement in blood pressure or cardiac output [25]. However, all patients were in an advanced disease state and were

ventilated and sedated, factors which may have precluded a beneficial effect. Investigators differ regarding methodology for measuring oxygen consumption, but the Edinburgh methodology seems more accurate. Nevertheless, the Edinburgh patients did not represent a cross-section of ALF. While NAC is widely used in the US in an oral preparation as Mucomyst® for acetaminophen overdoses, intravenous NAC infusion has not been available until recently, when it was approved by the US Food and Drug Administration for use in patients with acute acetaminophen hepatotoxicity. Intravenous NAC is not approved for use in patients with non-acetaminophen ALF in the United States because the limited data on its use for this condition was derived from uncontrolled observations.

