3.2 Research Design and Methods

N-acetylcysteine is being tested in a double blind, placebo-controlled, randomized trial as a treatment for non-acetaminophen ALF in children. The study drug or placebo will be given as a 7 day continuous intravenous infusion to children with acute liver failure not due to acute acetaminophen toxicity.

Vials of NAC will be available at each clinical center in the research pharmacy. Upon identification of a patient, study personnel (investigator or coordinator) will obtain informed consent, and then notify the research pharmacist of the patient's body weight, coma grade, and age. Orders for the solutions and the informed consent will be submitted to the clinical center's pharmacy, confirming that the patient is part of the study and outlining the timing for the infusion. The pharmacist will then log onto a web-based treatment allocation system maintained at the DCC which assigns therapy using a minimization scheme designed to balance treatment groups within a site by age (less than 2 years vs. at least 2 years) and coma score (0,1 vs. 2-4). The research pharmacist will prepare either a NAC solution as outlined below or 5% dextrose (placebo). The N-acetylcysteine will be added to 5% dextrose. The solution containing N-acetylcysteine will be administered as a continuous infusion at a dose of 150 mg/kg bodyweight in 5% dextrose over 24-hours for 7

consecutive days. Volumes will be adjusted for small children. The solution will be delivered to the clinical center with study labels which do not disclose the specific contents. Patients allocated to placebo will receive volume-matched 5% dextrose infusions. The NAC solution is colorless, so there should be no difficulty with inadvertent product identification. It may be possible to identify the solution by its smell, but all reasonable efforts will be made to exclude investigators from awareness of this information. A standard order form for the infusions will be inserted in the patient's chart to provide uniform orders at the study onset. Infusion of the study solution should take place as soon as possible following study entry (consent signed).

Participation in the NAC trial will not interfere with standard treatment for ALF including liver transplantation, if it is considered appropriate.

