3.3.3 Study Data Collection

All participants of the NAC trial must first be enrolled in the PALF registry and therefore all data collected as part of the registry will be available for these patients. Additional data collected for the NAC trial include:

- A form listing the patient's match to inclusion/exclusion criteria
- A daily log to capture the date and time infusion was started, the amount of the intravenous infusion, clinical measures, and adverse events. The date of treatment allocation, patient's weight and coma grade are also recorded on the log.

The daily log will be faxed upon completion to the DCC.

A parent may withdraw consent for participation in this research study at any time. In addition, a site principal investigator may withdraw a child from the study in circumstances related to either the parent or child's failure to cooperate fully with the conduct of the study, or the recognition of significant medical risks associated with the child's continued participation in this study. If a child's participation in this study is stopped, the reasons will be discussed with the parents and the child. Any research or medical information recorded for, or resulting from, the child's participation in this research study prior to the date that consent for child's participation was formally withdrawn may continue to be used by the investigators for the purposes described above.

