4.3 Inclusion/Exclusion Criteria – Pregnancy and Birth Control Statements

INCLUSION CRITERIA

1. Enrollment in PALF registry (use PT INR results from the most recent tests performed prior to plasma therapy, but no more than 72 hours prior to enrollment in the registry.)
2. Informed consent obtained from the patient (when patient is 14-17 years of age or <17 and developmentally able to sign his or her name and is without clinical encephalopathy), parent, or guardian

EXCLUSION CRITERIA

1. Acute Acetaminophen toxicity
2. Patient on N-acetylcysteine or received N-acetylcysteine during the course of this illness.
3. Pregnancy
4. Known malignancy
5. Patient is on a liver support device
6. Sepsis
7. Signs of cerebral herniation
8. Intractable hypotension defined as systolic BP < 85 mm Hg or hypotension that requires treatment with inotropic drugs, other than renal dosing dopamine

All female subjects of childbearing potential will receive a pregnancy test prior to enrollment. Pregnant females are not eligible for participation in the NAC trial.

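### The Section 6.4 pre-randomization checklist omits the exclusion for current or prior NAC that the synopsis and Section 4.3 require, so NAC-exposed children could be randomized as eligibility violations

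*Protocol*

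**What the plan says.** The design synopsis and Section 4.3 each give eight exclusions. The second in both is "Patient on N-acetylcysteine or received N-acetylcysteine during the course of this illness".

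Section 6.4 is headed "NAC checklist prior to entering and randomizing a patient". Its exclusions are numbered 1 to 7 without a gap. Item 1 is "Acute Acetaminophen toxicity" and item 2 is pregnancy; the NAC exclusion that stands between these two in Section 4.3 is absent. The other seven items match.

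The steps shown before allocation do not ask about NAC. Section 3.2 has study personnel "notify the research pharmacist of the patient's body weight, coma grade, and age". Section 6.4 tells them to "Fax a copy of the drug order form (with patient weight in kg, coma grade, and age"; the sample order form in Section 6.5 has fields for weight, age, coma grade and allergies, but none for NAC history. Section 3.3.3 lists, among the trial data, "A form listing the patient's match to inclusion/exclusion criteria". It does not show that form's content or say that it must be complete before treatment is assigned.

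On NAC use outside acetaminophen cases, Section 2.1.4 states that "intravenous NAC has been incorporated into the management strategy used at Kings and elsewhere as treatment for all acute liver failure". Section 3.1 describes only occasional use for such cases in the US, before FDA approval of the intravenous product, and adds that the practice was not generally accepted.

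**The concern.** A form meant for use just before randomization should carry every exclusion in the governing text. This one lacks the item that asks directly about exposure to the study drug. The acetaminophen item does not stand in for it, because the protocol itself reports NAC being given in liver failure of other causes. A child treated that way passes all seven checklist items.

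Two things are at stake. A placebo child who has had NAC, or is still receiving it, is not an untreated control, so the survival difference shrinks toward zero. In the NAC arm, open-label drug adds to the study drug. Safety is blurred in both arms, and Section 6.6 already concedes that NAC toxicity will be hard to recognize in these patients.

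**Working it through.** **Comparison of the lists**

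| Exclusion | Synopsis and 4.3 | Checklist 6.4 |
|---|---|---|
| Acute acetaminophen toxicity | 1 | 1 |
| Current NAC, or NAC in this illness | 2 | absent |
| Pregnancy | 3 | 2 |
| Malignancy | 4 | 3 |
| Liver support device | 5 | 4 |
| Sepsis | 6 | 5 |
| Cerebral herniation signs | 7 | 6 |
| Intractable hypotension | 8 | 7 |

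The unbroken numbering in 6.4 rules out a line lost in text extraction.

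**Inputs for the size**

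From Section 3.3.1: one-year survival 69% (placebo) and 86.5% (NAC), 92 per arm, 80% power, two-sided log-rank test, alpha 0.05 after the first monitoring revision. Not in the documents, so assumed: the share f of placebo children exposed to NAC (5%, 10%, 20%) and the fraction c of the planned benefit they carry (1 or 0.5). NAC-arm survival is held at 86.5%. Interim looks are not modelled.

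**Reproducing the plan's sample size**

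Hazard ratio = ln(0.865)/ln(0.69) = 0.391. Freedman's formula gives events = (1.960 + 0.842)² × ((1 + 0.391)/(1 − 0.391))² = 7.849 × 5.213 = 40.9, so 41. Mean event probability = (0.31 + 0.135)/2 = 0.2225, and 41/0.2225 = 184. The stated total reproduces.

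**Dilution**

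Diluted placebo survival: p = 0.69 + f × c × 0.175.

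Two-proportion power at n = 92 per arm is Φ[(0.865 − p − 1.960 × s0)/s1], with s0 = √(2m(1 − m)/n), m = (p + 0.865)/2, and s1 = √((p(1 − p) + 0.865 × 0.135)/n). With f = 0: s0 = 0.0613, s1 = 0.0600, giving Φ(0.914) = 82.0%.

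Freedman power is Φ[√E × (1 − h)/(1 + h) − 1.960], with h = ln(0.865)/ln(p) and E = 92 × ((1 − p) + 0.135). With f = 0: E = 40.94, giving Φ(2.802 − 1.960) = 80.0%.

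| Exposed share f | Carry-over c | Placebo survival | Difference (points) | Two-proportion power | Freedman power |
|---|---|---|---|---|---|
| 0 | – | 69.0% | 17.5 | 82.0% | 80.0% |
| 5% | full | 69.9% | 16.6 | 78.4% | 76.6% |
| 10% | full | 70.8% | 15.8 | 74.5% | 72.8% |
| 20% | full | 72.5% | 14.0 | 65.5% | 64.2% |
| 5% | half | 69.4% | 17.1 | 80.2% | 78.4% |
| 10% | half | 69.9% | 16.6 | 78.4% | 76.6% |
| 20% | half | 70.8% | 15.8 | 74.5% | 72.8% |

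The lowest row needs about 18 of 92 placebo children (0.20 × 92 = 18.4) to be exposed, all with the full benefit.

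**The case against.** The strongest reply is that the protocol does not admit these children. Eligibility is stated correctly in the synopsis and in Section 4.3, and those texts govern. This stands: a reader might infer that the checklist opens the trial to NAC-treated children, or that staff following it are bound to enroll them, but the documents support only a risk of eligibility violations.

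Other controls exist. Section 3.3.3 requires an eligibility form, Section 3.3.7 has site visitors review source documents for a sample of patients, and Section 4.5 has the DSMB review protocol deviations. This stands in part: the last two act after the fact, and the eligibility form is not shown to precede allocation.

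The acetaminophen exclusion stays on the checklist and removes the most obvious source of earlier NAC, so it is too strong to say that the treatment contrast loses its only protection. US use in other cases is described as occasional and not generally accepted, and the wider use reported in Section 2.1.4 comes without a rate.

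Full carry-over is a worst case. Section 2.1.4 justifies seven days of infusion because a shorter course may not be enough, which suggests that partial earlier exposure would carry less than the full benefit. The half-effect rows are there for that reason.

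The checklist's consent item also lacks the condition about encephalopathy in "developmentally able to sign his or her name and is without clinical encephalopathy), parent, or guardian". A reader might count this as a second route for excluded children. It is not: it bears on whether the child signs, parent or guardian consent remains, and no excluded child enters through it.

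**Conclusion.** The point holds as an internal contradiction in an operational form. The checklist drops a required exclusion, and no step shown before allocation is documented to catch the omission. The consequence is a possible, not a certain, entry of NAC-exposed children.

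The size is conditional. If 5% to 20% of placebo children were exposed, power would fall from 82.0% to between 78.4% and 65.5% with full carry-over, or to between 80.2% and 74.5% with half (two-proportion). The Freedman log-rank figures fall from 80.0% to between 76.6% and 64.2%, or to between 78.4% and 72.8%. Neither the exposure share nor the carry-over comes from the documents, so the table must not be read as an estimate of power actually lost. It shows that a design planned at 80% has little room for such exposure.

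**What to change.** Restore the NAC exclusion so that the exclusion list in Section 6.4 is identical to that in Section 4.3. Query sites about NAC exposure before randomization in every child already enrolled, record any violations, and keep those children in the primary analysis. At the first interim look 79 of 184 were enrolled (Section 3.3.1), so 184 − 79 = 105 entries were still to come at that point.

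As a separate consistency correction, unrelated to dilution, align the consent wording in 6.4 with 4.3.

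A required NAC field in the web allocation system and a sensitivity analysis without exposed children are both optional.

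The cost is one corrected form and one data query to sites. The sample size, survival assumptions and boundaries are unchanged.
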